9.2.1 Exclusion Criteria for Diagnostic Performance Analysis

Samples meeting any of the following criteria in the course of the study will be excluded from the primary analyses of Xpert MTB/XDR accuracy:

- no valid result for NGS for relevant gene region or Xpert MTB/XDR,
- smear-positive/culture negative,
- single positive culture with ≤ 20 colonies (LJ) or time to positivity > 28 days (MGIT),
- culture positive but no MTB complex identification available,
- specimens with growth of mycobacteria other than MTB complex only

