7.1 Reference Standard Test and Index Test Procedures

A composite reference standard of phenotypic DST and NGS will be used for resistance detection to ensure high confidence in the reference standard for this study. Phenotypic MGIT DST and targeted NGS will be performed on the culture isolate for each clinical sample. MGIT DST will be done on site to determine culture drug-susceptibility to INH, ETH, moxifloxacin, levofloxacin, AMK, KAN and CAP at the revised WHO critical concentrations¹⁵. Targeted NGS of the gene regions included in the Xpert MTB/XDR assay will be performed on DNA extracted from the cultured sample, which will be sent to a SNRL for NGS, or sequenced locally using primers specific for the gene regions included in the assay. The output for both phenotypic DST and NGS results are automated, and require no manual operator interpretation. Testing results, when obtained, will be input onto the laboratory CRF.

The index test will be performed on both the direct clinical sample as well as the culture isolate, to ensure high Xpert MTB/XDR diagnostic performance direct from sputum and to provide a basis for comparison if any discordants are seen between the initial Xpert MTB/XDR result and the phenotypic DST and additional molecular test results (NGS and LPA). The output for the Xpert MTB/XDR assay is automated and does not require manual interpretation. As with the reference test, all Xpert test results will be noted on the laboratory CRF.

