9.2.2 Definitions for Diagnostic Performance Analysis

TEST RESULT	DESCRIPTION
Phenotypic Drug*-resistant	Culture-positive and growth for Drug* in conventional DST testing.
Phenotypic Drug*-sensitive	Culture-positive and no growth for Drug* in conventional DST testing
Genotypic Drug*-resistant	NGS identifies mutations recognized to be associated with resistance (defined based on consultation with WHO prior to analysis)
Genotypic Drug*-sensitive	NGS identifies no mutations recognized to be associated with resistance (defined based on consultation with WHO prior to analysis)
Composite reference standard Drug*-resistant	If Phenotypic Drug*-sensitive but NGS identifies mutations recognized to be associated with Drug* resistance for the respective gene regions, the composite reference standard will be considered Drug*-resistant. If Phenotypic Drug*-resistant but NGS does not identify mutations recognized to be associated with Drug* resistance for the respective gene regions, the composite reference standard will be considered Drug*-resistant (as mutations will be assumed outside of the region sequenced).

Composite reference standard Drug*-sensitive | If Phenotypic Drug*-sensitive and NGS shows either no mutations or only mutations that are not associated with Drug* resistance for the respective gene regions.

* Drug: INH, ETH, FQ (moxifloxacin and levofloxacin for phenotypic DST), AMK, KAN or CAP

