Appendix 4: Sample Requirement to Achieve Target Sample Size

	MTB+ group*		Additional RIF-R group		TOTAL
Samples Tested	100%	360	100%	400	760
Invalid Xpert Ultra results	1%	4	1%	4	8
Culture-contaminated	10%	36	10%	40	76
Molecular-test non-determinant*	10%	36	10%	40	76
Included**	79%	284	79%	316	600
INH-resistant	29%	82	99%	313	395
INH-sensitive	71%	202	1%	3	205
FQ-resistant	5%	14	25%	79	93
FQ-sensitive	95%	270	75%	237	507
AMK/CAP-resistant	2%	6	9%	28	34
AMK/CAP-sensitive	98%	278	91%	288	566
KAN-resistant	1%	3	21.5%	68	71
KAN-sensitive	99%	281	78.5%	248	529

*Assume 23% of TB-positive samples are RIF-R based upon previous studies and data from these regions^{11,13}.

**We assume 29% INH resistance, 5% FQ resistance and 1-2% second-line injectable (AMK, KAN and CAP) resistance among TB-positive patients based upon previous studies and data from these regions^{11,13}. Testing 284 TB-positive specimens (based on Xpert MTB/RIF and Ultra-testing) would then be expected to yield 82 INH-resistant but only 14 FQ-resistant specimens and 3-6 second-line injectable-resistant specimens (limiting factor in sample size calculations). This allows for determination of Xpert MTB/XDR performance for INH resistance detection as a reflex test to any TB-positive result, but is not sufficient for determination of Xpert MTB/XDR performance for second-line resistance detection. To efficiently get to a sufficient number of second-line resistant samples, we will supplement this by testing 316 additional RIF-resistant samples. To account for contaminated cultures and invalid/non-determinant Xpert MTB/RIF or Ultra, NGS and Xpert MTB/XDR results, we would inflate these numbers by 21%, leading to a total of 360 TB-positive and 400 additional RIF-resistant samples, i.e. a total of 760 patient samples tested in this study.

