3.2 Analysis datasets

Describe the datasets that will be used in the analysis, like the examples below.

- ITT (Intention-To-Test) all subjects successfully enrolled in the study

- MITT (Modified-Intention-To-Test) all subjects in ITT for whom at least one test result is available, but not all (e.g. composite reference missing)
- PP (Per-Protocol) all subjects in ITT for whom results for all tests (Xpert MDR/XDR and composite reference standards) are available (complying with the protocol)
- QUEST (Questionnaire evaluation) all personnel who provided valid responses to the Xpert MTB/XDR Clinical Study User Appraisal Questionnaire

Samples meeting any of the following criteria in the course of the study will be excluded from the primary analyses of Xpert MTB/XDR accuracy:

- no valid result for NGS for relevant gene region or Xpert MTB/XDR,
- smear-positive/culture negative,
- single positive culture with ≤ 20 colonies (LJ) or time to positivity > 28 days (MGIT),
- culture positive but no MTB complex identification available,
- specimens with growth of mycobacteria other than MTB complex only

4 Description of statistical methods

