4.2 Analysis of the primary outcome(s)

The primary objectives 1.1, 1.2 and 1.3 will be analysed with the methodology described in section 4.1.

Outcome 1.1

Estimates of sensitivity and specificity of Xpert MTB/XDR will be calculated, for INH and ETH resistance detection with phenotypic DST and *katG*, *fabG1*, *ahpC* and *inhA* sequencing results as a composite reference standard (see Appendix). This outcome will be evaluated on the PP population.

Outcome 1.2

Estimates of sensitivity and specificity of Xpert MTB/XDR will be calculated, for fluoroquinolone resistance detection, with phenotypic DST and *gyrA* and *gyrB* sequencing results as a composite reference standard (see Appendix). This outcome will be evaluated on the PP population.

Outcome 1.3

Estimates of sensitivity and specificity of Xpert MTB/XDR will be calculated, for second-line injectable resistance detection, with phenotypic DST and *rrs* and *eis* sequencing results as a composite reference standard (see Appendix). This outcome will be evaluated on the PP population.

Outcome 1.4

Assess Xpert MTB/XDR operational aspects and ease of use, including Xpert MTB/XDR non-determinant rates.

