FQ-resistant	NGS of gyrA and gyrB detects ≥ 1 mutation associated with MFX resistance and MGIT culture is MFX drug-resistant at the critical concentration.
AMK-resistant	NGS of rrs and eis detects ≥ 1 mutation associated with AMK resistance and MGIT culture is AMK drug-resistant at the critical concentration.
KAN-resistant	NGS of rrs and eis detects ≥ 1 mutation associated with KAN resistance and MGIT culture is KAN drug-resistant at the critical concentration.
CAP-resistant	NGS of rrs detects ≥ 1 mutation associated with CAP resistance and MGIT culture is CAP drug-resistant at the critical concentration.
INH-susceptible	NGS of katG , fabG1 , ahpC and inhA does NOT detect any mutation associated with INH resistance and MGIT culture is INH-susceptible at the critical concentration.
ETH-susceptible	NGS of inhA does NOT detect any mutation associated with ETH resistance and MGIT culture is ETH-susceptible at the critical concentration.
FQ-susceptible	NGS of gyrA and gyrB does NOT detect any mutation associated with MFX resistance and MGIT culture is MFX-susceptible at the critical concentration.
AMK-susceptible	NGS of rrs and eis does NOT detect any mutation associated with AMK resistance and MGIT culture is AMK-susceptible at the critical concentration.
KAN-susceptible	NGS of rrs and eis does NOT detect any mutation associated with KAN resistance and MGIT culture is KAN-susceptible at the critical concentration.
CAP-susceptible	NGS of rrs does NOT detect any mutation associated with CAP resistance and MGIT culture is CAP-susceptible at the critical concentration.

Table 4 Definition of composite reference standards

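### DST-resistant samples without valid NGS are excluded although protocol 9.2.2 already makes them resistant; SAP Table 4 disagrees, so reconcile the definitions, then classify per drug

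*Protocol*

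**What the plan says.** **Exclusion.** Protocol 9.2.1 removes samples with "no valid result for NGS for relevant gene region or Xpert MTB/XDR" from the primary accuracy analyses, and SAP 3.2 repeats the bullet. Neither makes an exception for samples that are resistant on phenotypic DST. SAP 3.2 also limits the per-protocol set to subjects "for whom results for all tests (Xpert MDR/XDR and composite reference standards) are available (complying with the protocol".

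**Composite rule, first form.** Protocol 9.2.2 and SAP Table 3 cover the discordant case "If Phenotypic Drug*-resistant but NGS does not identify mutations recognized to be associated with Drug* resistance for the respective gene regions" and call it resistant. A DST-sensitive sample with a listed mutation is resistant too. A sensitive call needs DST sensitivity and a reading in which "NGS shows either no mutations or only mutations that are not associated with Drug* resistance for the respective gene regions".

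**Composite rule, second form.** SAP 4.2 defines primary outcomes 1.1 to 1.3 by "sequencing results as a composite reference standard (see Appendix). This outcome will be evaluated on the PP population". The table in that Appendix, Table 4, needs both components for a resistant call; for amikacin it asks for a "mutation associated with AMK resistance and MGIT culture is AMK drug-resistant at the critical concentration".

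**Planned losses.** Protocol Appendix 4 states: "To account for contaminated cultures and invalid/non-determinant Xpert MTB/RIF or Ultra, NGS and Xpert MTB/XDR results, we would inflate these numbers by 21" per cent. That is 1% invalid Ultra, 10% contaminated culture and 10% molecular non-determinant. The last item pools NGS with Xpert and is not split.

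**The concern.** Under 9.2.2 the plan lets DST overrule an NGS result that reads the region and finds nothing, yet discards the same DST result when NGS is merely absent. NGS is needed only for a susceptible call. Every DST-resistant sample lost this way belongs to the sensitivity denominator, where second-line resistance is already sparse (34 for AMK and CAP).

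A related gap is partial failure. Isoniazid rests on four regions (Protocol Table 1). If *katG* carries a listed mutation and *ahpC* cannot be read, the class is settled under 9.2.2; if DST is also resistant, it is settled under Table 4 as well. The exclusion bullet does not say whether one unreadable region removes the sample.

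The larger stake is bias. Xpert and NGS read similar gene regions (Protocol 5.3.3). NGS is run on the culture isolate, and the isolate's Xpert result is the one used when sputum and isolate differ (Protocol 9.2). If NGS fails more often in samples that Xpert calls falsely susceptible, the exclusion raises estimated sensitivity. No planned analysis would show this: the SAP has no missing-data analysis beyond the exclusion list, and its section 9 rules out exploratory work.

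**Working it through.** **1. Class of a DST-resistant sample, by NGS result**

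| NGS | Protocol 9.2.2 / SAP Table 3 | SAP Table 4 |
|---|---|---|
| Listed mutation | resistant (implied) | resistant |
| Valid, no listed mutation | resistant | in neither class |
| No valid result | resistant on either possible reading | in neither class |

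The exclusion therefore discards a known class under the first definition and not under the second.

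**2. The plan's own figures.** 284/(1 − 0.21) = 359.5, taken as 360; 316/0.79 = 400; total 760. Appendix 4 percentages applied to 284 and 316 give 395 INH-, 93 FQ-, 71 KAN- and 34 AMK/CAP-resistant samples, as stated. Table 2 uses the Wilson score interval with continuity correction:

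limits = [2np + z² ∓ 1 ∓ z√(z² ∓ 2 − 1/n + 4p(n(1 − p) ± 1))] / [2(n + z²)], upper signs for the lower limit.

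For n = 34, p = 0.90, z = 1.96:
- lower = (64.04 − 8.23)/75.68 = 73.7%
- upper = (66.04 + 7.45)/75.68 = 97.1%
- width 23.4 points, against the stated 74 to 97.

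The other sensitivity rows agree to rounding.

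**3. Resistant samples recoverable.** Molecular non-determinants are 36 + 40 = 76. Expected resistant among them:
- AMK/CAP: 36 × 0.02 + 40 × 0.09 = 4.3
- KAN: 36 × 0.01 + 40 × 0.215 = 9.0
- FQ: 36 × 0.05 + 40 × 0.25 = 11.8
- INH: 36 × 0.29 + 40 × 0.99 = 50.0

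The NGS share of the 76 is not given. The table assumes that all, or half, are NGS failures with a valid Xpert result, and that every resistant one is DST-resistant, so these are upper values for each share.

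| Drug | Planned n (CI width) | Half are NGS failures | All are NGS failures |
|---|---|---|---|
| AMK/CAP | 34 (23.4) | 36 (22.6) | 38 (22.0) |
| KAN | 71 (15.5) | 75 (15.1) | 80 (14.5) |
| FQ | 93 (13.4) | 99 (12.9) | 105 (12.5) |
| INH | 395 (6.2) | 420 (6.0) | 445 (5.8) |

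At a one-tenth share, n is 34, 72, 94 and 400. Appendix 4 and Table 2 have no ethionamide row, so no size can be given for that drug.

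**4. Possible bias.** With 90% sensitivity in kept samples, L resistant samples lost and sensitivity s in them, overall sensitivity = (0.90n + sL)/(n + L). For AMK/CAP at a half share, L = 2.16:
- s = 90%: 90.0%
- s = 70%: (30.6 + 1.51)/36.16 = 88.8%
- s = 50%: (30.6 + 1.08)/36.16 = 87.6%

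If all 76 are NGS failures (L = 4.32), the last two become 87.7% and 85.5%. Other drugs agree within 0.1 point, because lost and kept samples are in nearly the same ratio. The values of s are assumptions; the documents give none.

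**5. Tilt from one-sided recovery.** Suppose NGS fails at random. Let q be the DST-resistant share of the resistant group, g the amount by which Xpert sensitivity is higher in mutation-only samples than in DST-resistant ones, and r the ratio of lost to kept samples. Adding back only the DST-resistant ones moves sensitivity by −rq(1 − q)g/(1 + rq). With r at most 76/600 = 0.127 and q = 0.5, close to the worst case, this is −0.127 × 0.25g/1.063 = −0.03g. An assumed gap of 10 points gives about 0.3 points.

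**The case against.** The strongest reply is that the SAP's primary outcomes point to Table 4, under which a DST-resistant sample without NGS has no class, so excluding it is consistent. That stands. A reader might infer that the plan's composite rule already fixes these samples as resistant; it does so only in protocol 9.2.2 and SAP Table 3.

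Second, the loss is budgeted. Table 2 is net of the 10% allowance, so the rule causes no shortfall against plan. That also stands. NGS failures may be fewer still, since leftover samples are kept for repeat testing (Protocol 7).

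Third, a reader might infer that NGS failure goes with Xpert failure, because DNA may be "sequenced locally using primers specific for the gene regions included in the assay". The documents do not support this. That phrase describes one of two options, the other being shipment to a reference laboratory. Shared gene regions are not shared primer sites, and no passage says that whatever defeats NGS yields a valid but false Xpert call. Samples with no valid Xpert result stay excluded by the same bullet, so a changed NGS rule cannot recover them. The link is plausible and should be tested.

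Fourth, one can construct a drop for INH to 355.5/405 = 87.8% by adding 10 Xpert-negative samples and no Xpert-positive ones. That is an adverse scenario, not an estimate. With the other 15 of 25 lost samples counted as Xpert-positive, the figure is 370.5/420 = 88.2%.

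Fifth, requiring both components treats resistant and susceptible samples alike, whereas recovery is one-sided and raises apparent prevalence, which would distort the secondary predictive values (Protocol 9.2.4). This is a fair cost. Step 5 shows that it is small for sensitivity, and the predictive values can be kept on complete pairs.

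**Conclusion.** The point holds in limited form and is worth correcting. Protocol 9.2.1 and SAP 3.2 exclude samples whose class is already settled under protocol 9.2.2 and SAP Table 3, and SAP Table 4 conflicts with that definition. The exclusion cannot be judged or repaired until one definition governs.

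The precision gain is small: at most 1.4 points of interval width for AMK/CAP and 1 point or less for the other drugs. Possible bias is the better reason to act. It ranges from zero, if lost samples behave like kept ones, to 1.2 or 2.4 points when half of the non-determinants are NGS failures and Xpert sensitivity in them is 70% or 50%. The NGS share and those sensitivities are assumptions. A reader might also infer that one unreadable region definitely removes a sample; the text leaves that open, so it is an ambiguity to settle rather than an established exclusion.

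**What to change.** 1. Adopt the either-positive rule of protocol 9.2.2 throughout. Bring SAP Table 4 and the per-protocol definition into line. Settle the region lists at the same time: for amikacin, Protocol Table 1 names *rrs* and SAP Table 4 names *rrs* and *eis*.
2. In protocol 9.2.1 and SAP 3.2, replace the NGS exclusion with a per-drug rule among samples with a valid Xpert result:
   - *Resistant*: DST is resistant or any relevant region carries a listed mutation, even if the other component or another region is missing.
   - *Susceptible*: DST and all relevant regions are valid and negative.
   - *Unclassifiable*: anything else, excluded for that drug only.
3. Report the complete-pair analysis alongside.
4. Pre-specify a cross-tabulation of NGS failure by DST and Xpert result, which tests the suspected link directly.
5. Compute positive and negative predictive values on complete pairs only.

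The cost is wording in both documents and two tables, with no new samples or tests. The downside is a slight tilt of the resistant group towards DST-resistant samples, so a difference of a few tenths of a point between the two analyses should not by itself be read as bias.

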9.2.2 Definitions for Diagnostic Performance Analysis

TEST RESULT	DESCRIPTION
Phenotypic Drug*-resistant	Culture-positive and growth for Drug* in conventional DST testing.
Phenotypic Drug*-sensitive	Culture-positive and no growth for Drug* in conventional DST testing
Genotypic Drug*-resistant	NGS identifies mutations recognized to be associated with resistance (defined based on consultation with WHO prior to analysis)
Genotypic Drug*-sensitive	NGS identifies no mutations recognized to be associated with resistance (defined based on consultation with WHO prior to analysis)
Composite reference standard Drug*-resistant	If Phenotypic Drug*-sensitive but NGS identifies mutations recognized to be associated with Drug* resistance for the respective gene regions, the composite reference standard will be considered Drug*-resistant. If Phenotypic Drug*-resistant but NGS does not identify mutations recognized to be associated with Drug* resistance for the respective gene regions, the composite reference standard will be considered Drug*-resistant (as mutations will be assumed outside of the region sequenced).

Composite reference standard Drug*-sensitive | If Phenotypic Drug*-sensitive and NGS shows either no mutations or only mutations that are not associated with Drug* resistance for the respective gene regions.

* Drug: INH, ETH, FQ (moxifloxacin and levofloxacin for phenotypic DST), AMK, KAN or CAP

9.2.3 Additional Characteristics Assessed

Secondary analyses will investigate assay diagnostic performance between important subgroups, including: Xpert MTB/XDR direct versus indirect performance (on direct versus cultured samples), performance between sites, by smear result, by gene target, performance compared to Hain MTBDR*plus* and MTBDR*sl* assays, performance by reflex test to Xpert MTB/RIF or Ultra result, and performance by patient HIV and pre-treatment status. Detailed definitions for diagnostic test results are given in Appendix 5: Definitions of Diagnostic Test Results.

9.2.4 Efficacy Analyses

Endpoint	Statistical Analysis Methods
Primary	
 • Sensitivity • Specificity • Data summaries
Secondary	
 • Chi-squared • Sensitivity • Specificity • Positive Predictive Value • Negative Predictive Value

